A mixed methods pilot study exploring the feasibility, acceptability and potential benefits to Mentalisation Based Treatment for Older Adults with Complex Emotional Needs

MBT for socially isolated older adults with personality disorder This protocol has regard for the HRA guidance and order of content

A mixed methods pilot study exploring the feasibility, acceptability and potential benefits to Mentalisation Based Treatment for Older Adults with Complex Emotional Needs

Overall Aim: To enhance our understanding of whether MBT is an acceptable and feasible intervention for older adults with personality disorders. In addition, the aim of the study is to determine any potential benefits to MBT in older adults.

Hypothesis: MBT is acceptable and feasible as an intervention for OAs with CEN. It has potential cost saving, quality of life improving and risk reducing benefits. Some adaptations are required.

SHORT TRIAL TITLE - MBT for socially isolated older adults with personality disorder

PROTOCOL VERSION NUMBER AND DATE V 1.4 07.08.25

RESEARCH REFERENCE NUMBERS

IRAS Number: 341968

SPONSORS Number: x750

SPONSOR

Greater Manchester Mental Health NHS Foundation Trust

Collaborators

University of Tilburg

SIGNATURE PAGE

The undersigned confirm that the following protocol has been agreed and accepted and that the Chief Investigator agrees to conduct the trial in compliance with the approved protocol and will adhere to the principles outlined in the Medicines for Human Use (Clinical Trials) Regulations 2004 (SI 2004/1031), amended regulations (SI 2006/1928) and any subsequent amendments of the clinical trial regulations, GCP guidelines, the Sponsor's (and any other relevant) SOPs, and other regulatory requirements as amended.

I agree to ensure that the confidential information contained in this document will not be used for any other purpose other than the evaluation or conduct of the clinical investigation without the prior written consent of the Sponsor.

I also confirm that I will make the findings of the trial publically available through publication or other dissemination tools without any unnecessary delay and that an honest accurate and transparent account of the trial will be given; and that any discrepancies and serious breaches of GCP from the trial as planned in this protocol will be explained.

For and on behalf of the Trial Sponsor:	
Signature:	Date:
	//
Name (please print):	
Position:	
Chief Investigator:	
Signature:	Date:

13 ETHICAL AND REGULATORY CONSIDERATIONS	
14. DISSEMINATION POLICY	
15. REFERENCES	
16. APPENDICIES	

ii. LIST OF ABBREVIATIONS

Define all unusual or 'technical' terms related to the trial. Add or delete as appropriate to your trial. Maintain alphabetical order for ease of reference.

AE Adverse Event

CMHT Community Mental Health Team

CI Chief Investigator
CRF Case Report Form
CTU Clinical Trials Unit

DMC Data Monitoring Committee

GMMH R&I Greater Manchester Research and Innovation

ICF Informed Consent Form

MBT Mentalisation Based Treatment

PI Principal Investigator

PIS Participant Information Sheet

QA Quality Assurance
QC Quality Control
QP Qualified Person

REC Research Ethics Committee

SAE Serious Adverse Event

SCED Single Case Experimental Design

SOP Standard Operating Procedure

TSC Trial Steering Committee

iii. TRIAL SUMMARY

Trial Title	Multiple Single Case Series Design study into the efficacy of Mentalisation Based Treatment for treating personality functioning and social isolation in Older Adults with a diagnosis of Personality Disorder			
Internal ref. no. (or short title)	MBT for socially isolated olde	r adults with personality disorder		
Clinical Phase				
Trial Design	Multiple Single Case Series D	esign		
Trial Participants	Older adults (65+)			
	Personality disorders			
Planned Sample Size	10-14			
Treatment duration	24 months	24 months		
Follow up duration	6 months			
Planned Trial Period	3 years			
	Objectives	Outcome Measures		
Primary	Measure change in	LPFS 2.0		
	personality functioning and social isolation	Social Isolation 4.0		
Secondary	Quality of life	ReQoL		
	Satisfaction	Dialogue		
	Suicidality CSRSS			
Investigational Medicinal Product(s)	N/A			
Formulation, Dose, Route of Administration	N/A			

iv. FUNDING AND SUPPORT IN KIND

Support in Kind	FINANCIAL AND NON FINANCIALSUPPORT GIVEN
NHS - Greater Manchester Foundation Mental Health Trust	Nonfinancial: time of [name], [name], [name],
Tilburg University/GGz Breburg	Nonfinancial: time of [name] and [name]
Greater Manchester Mental Health Research and Innovation Team	Nonfinancial: time of Research and Innovation team

v. ROLE OF TRIAL SPONSOR

Greater Manchester Mental Health Foundation Trust Research and Innovation Team. The role of this sponsor is to provide assurances that the study design accords with HRA processes, that the research is sustainable and achievable, and that it is safe and effective for participants.

vi. ROLES AND RESPONSIBILITIES OF TRIAL MANAGEMENT COMMITEES/GROUPS & INDIVIDUALS

Trial Management Committees

• Trial Management Group

The Trial Management Group should meets monthly. It is comprised of the academic sponsors at Tilburg University, and the members of the treatment and research team. It's function is to ensure all practical details of the trial are progressing well and working well and everyone within the trial understands them. The team also considers the ethical concerns of the trial, and the overall design.

vii. Protocol contributors

Name	Contact
[name],	[contact],
	[name]
[name]	, [contact]
[name]	, [contact]
[name]	, [contact]
[name],	[contact]
[name],	[contact]
[name],	[contact]
[name] - Lived Experience Contributor	N/A
[name] – Lived Experience Contributor	N/A

The above contributors have supported the planning of the project. All members excluding [name] are members of the trial steering committee. All members excluding [name] will also support the writing, dissemination and analysis of final anonymised data.

viii. KEY WORDS:

Older adults, personality disorder, social isolation, complex emotional needs, social isolation

ix. TRIAL FLOW CHART

Phase 1 - consent.

Participant identified by local CMHT or Therapy hub

Participant contacted to gain consent to view PIS

Participant meets research team. PIS given to participant.

Fortnightly supervision provided by contributors. TSG meets 6 weekly with contributors until study end.

Participant waits 7 days before they are asked to give consent

Participant asked to give informed consent

Participant does not consent to research and declines treatment

Referrer notified. Any risks clearly explained to participant and referring team.

Participant does not consent to research but wishes to receive MBT

Participant is provided **MBT** if clinically indicated. They do not form part of the research study. Participant is asked if we can use data relating to dropout and if they will consent to an exit interview.

Participant consents to research and wishes to receive MBT

Participant is offered MBT assessment if clinically indicated. They form part of the research study.

Phase 2 - Assessment

Participant is offered MBT assessment

[figure not shown]

Participant is offered 3 screening appointments, in line with standard practice. These appointments explain MBT, and determine whether MBT is clinically indicated.

Participant is not suitable for MBT

Referrer notified. Any risks clearly explained to participant and referring team.

Structured Clinical Interview for DSM-V Personality Disorder administered using both the screening tool and full interview.

Participant does not meets diagnostic criteria

Participant meets diagnostic criteria, or is 1 criterium below the diagnostic criteria.

Participant is invited to begin the treatment phase. Initial qualitative interviews completed.

Phase 3 - Treatment

Participant is invited to attend the MBT-Introductory group for 12 weeks.

Following MBT-I. Participants have an 8-week waiting period. This is the baseline phase. During this phase further assessment work is completed. Data collection via PROMIS questionnaires begins at the start of this phase on a weekly basis.

Participants are provided 18 months of MBT treatment. They are provided a weekly individual and group appointment. Data collection continues weekly.

After 18 months the participants end MBT. A review is completed with the participant, their consultant psychiatrist, and MBT practitioner.

Follow-up phase begins

Phase 4 – Follow-up

Participant begins follow-up phase

Each participant is asked to complete a short qualitative interview. This interview focuses on the acceptability of the intervention

Participants are contacted each week to complete the PROMIS questionnaires. 6 months of follow-up will be completed.

At the end of the follow-up period, participants are reminded of contact details for relevant individuals and informed of further details regarding future dissemination plans.

Study ends at the completion of all follow-up appointments.

Contributors support writing, dissemination and analysis of final anonymised data

1 BACKGROUND

Mentalisation Based Treatment (MBT) is an evidence-based approach for treating Borderline Personality Disorder in adults (Bateman and & Fonagy, 2009). It emphasizes building a therapeutic alliance, fostering epistemic trust, and nurturing the mentalizing process (Bateman & Fonagy, 2016). MBT is a structured psychological therapy program that includes weekly individual and group sessions.

Individuals with personality disorder often exhibit challenges in the mentalizing process (Bateman & Fonagy, 2010). Older adults, when assessed using the Mentalization Questionnaire, appear to have mentalizing strengths and weaknesses similar to younger adults, but with slightly more pronounced deficits in theory of mind (Brewer, et al, 2007)

Clinical populations of older adults also show significant mentalizing deficits compared to non-clinical older adult groups (Meinolf & Schulz, 2022). Given MBT's proven efficacy in enhancing mentalizing in younger populations and the observed mentalizing deficits in older clinical groups, MBT is a pertinent research area. While older adults seem to have broadly similar mentalizing deficits as younger adults, there's no evidence indicating they benefit from the same treatments. Anecdotal evidence suggests older adults may have distinct mentalizing needs, including increased suppression (Brummer et al., 2013), a higher prevalence of obsessive, avoidant, or dependent traits (Brudley, 2021), and potential physical or cognitive decline (Penders et al., 2020).

2 RATIONALE

To date, there have been no studies assessing the efficacy of MBT in older populations. Research on treatments for older adults with personality disorder is limited (van Alphen et al., 2015). While there is a growing interest in studying older adults with personality disorder, much of the research primarily focuses on assessment (Penders et al., 2020). However, studies on the effectiveness of Dialectical Behaviour Therapy (Lynch et al., 2007) and Schema Therapy (Videler et al., 2018; Videler et al., 2021; Khasho et al, 2023, Veenstra-Spruit et al., 2024) for older adults with personality disorder have been conducted and show potential.

The cost per person of outpatient treatment and prescribing is significantly higher per OA with CEN than any other age group with the same condition (King's Fund, 2008) Effective treatment of CENs in later life represents potential cost savings (Le, 2021), due to the burden associated with service use (King's fund, 2008), the prevalence of suicide (ONS, 2021), self-neglect (Sanders, 2022), and abuse (WHO, 2023).

The aims of this project accord with the NHS long term plan (NHS, 2019), which has clearly set out targets to increase the access for evidence-based treatment for OAs. This study will widen the access to research and treatment for OAs, develop an adapted model of care for OAs, and inform the design of a future RCT. Following this study, I plan to research the efficacy of a shortened version of MBT, which would be more cost effective, and feasible for use in primary care. This work, and future related projects will help to shape policy as well as NICE guidelines pertaining to treatment of CEN in OAs.

Interventions for OAs with CEN require significant adaptation, but there is no literature exploring systematically what sorts of adaptations OAs with CEN require. This study will provide necessary insight into how MBT, and CEN treatments more broadly, should be adapted for OAs..

When the research was discussed with our PPIE group, they said, "we are often forgotten about", "I think its good that NHS is looking more into our problems", "this is relevant to my wife who I care for", "this is relevant to me", and "I definitely think this is a good project". With regards to MBT, one group member said that he feels more "useful" to society and his family as his functioning has improved following treatment. Another said he felt "less of a burden" and "more content with life" after receiving MBT.

2.1 Assessment and management of risk

The service which is being used for the study is an existing MBT service. No risks have been associated with participants being part of the programme. The treatment is a talking therapy, with no medical intervention. A large RCT which investigated the efficacy of MBT in working age adults found no adverse effects, or risks to participants. The intervention reduced incidents of self-harm, suicidal behaviour and hospital admission, and as such was risk reducing in that population (Bateman & Fonagy 2009).

Preliminary service evaluation data of the service which is to be studied indicated improvements in quality of life, personality functioning, social isolation, satisfaction, and suicidality (Jordan, 2023).

If risk incidents do arise, then the process of the therapy will be followed. This involved discussing and managing the cause of the risk in the treatment. Additionally the team will follow the NICE guidelines on the management of self-harm, which include

- Consideration to lethal means
- Problem solving cause of the crisis
- Increasing external support
- Validating and generating hope
- Ensuring timely follow up by team or wider care team
- Troubleshooting
- Adhering to care plan

Following any risk event, the participants care coordinator will be contacted, with the participant's consent. Where consent is withdrawn, the team will take advice by the GMMH safeguarding service as to whether there is grounds to break confidentiality. This will be communicated to the participant, care team and study sponsor.

3 OBJECTIVES AND OUTCOME MEASURES/ENDPOINTS

3.1 Primary Outcomes:

To evaluate the feasibility of MBT in older adults

Feasibility of the study will be assessed by examining recruitment rate, consent rate, proportion of participants lost to follow-up, number of sessions attended, and drop out rate. The detailed table in the

upload section of this application illustrates the feasibility aims. This table shows the aims for the study with regard to above metrics.

To evaluate the acceptability of MBT in older adults

Acceptability will be evaluated by using Semi-structured qualitative interviews. These interviews will be delivered by 2-3 lived-experience researchers. I aim to determine what adaptations are indicated, integrating findings from qualitative and quantitative analysis to assess the feasibility of MBT. This will result in a fully adapted intervention.

I will use the Theoretical Framework for Acceptability to ensure the interviews assess acceptability. The interviews will focus on the seven constructs of acceptability (Paynter et al 2023):

To evaluate the change in personality functioning and social isolation in older adults undergoing MBT.

Changes in Personality Functioning Using the Level of Personality Functioning Scale Brief Form (LPFS-BF 2.0)

The LPFS 2.0 is a 12-item questionnaire that assesses personality functioning on a 4-point scale (Bender et al., 2011). This tool offers insights into the severity of personality pathology and sheds light on self and interpersonal functioning (Hutsebaut et al., 2016). The LPFS 2.0 has been empirically validated for older adults and has proven valuable in assessing personality functioning in this demographic (Stone et al., 2021).

To ensure adequate statistical power, the LPFS-BF will be administered weekly, following each individual therapy session. This frequent data collection will enhance the reliability of observed changes.

Loneliness Measured by the Social Isolation Short Form 4a

The Social Isolation Short Form 4a, derived from the more extensive UCLA Loneliness Scale, is a globally recognized tool for measuring loneliness. It aligns with the UK's Office for National Statistics recommendations for assessing loneliness (ONS, 2018) and has demonstrated reliability in gauging social isolation. Although a more detailed version, the Social Isolation Short Form 8a, is available and offers increased reliability, its length might be burdensome for weekly assessments. Therefore, this study proposes using the shorter form as a primary outcome. It will be administered weekly, following each individual therapy session.

Service use

To determine if there is any potential cost saving for the NHS, we will ask participants to consent to the research team to take a record of:

- Unplanned contact with the service
- A and E attendances
- Crisis line contacts
- Days in psychiatric hospital
- Days spent in general hospital

Self harm and suicidal behaviour

To determine if there has been any reduction in self-harm and suicidal behaviour, we will ask participants to consent to the research team to take a record of:

- Incidents of self-harm recorded in the clinical record
- Incidents where the participant has engaged in self-injury or self-neglect where their intent was to cause life threatening injury.

3.2 Secondary Outcome:

Other Routine Outcome Measures: Quality of Life, Patient Satisfaction, and Suicidality

In addition to the weekly assessments, participants will complete three other questionnaires at start of baseline, start of treatment, 6 months, 12 months, 18 months into the treatment and at the end of follow-up. These scales evaluate quality of life (ReQol), patient satisfaction (Dialogue), and suicidality (Columbia Scale).

*ReQoI: The Recovering Quality of Life (ReQoI-10) scale tracks perceived changes in 'quality of life' over time. This 10-item scale is validated for individuals aged 16 and above. Scores range between 1 and 5, and a shift of 5 points on the scale indicates 'significant improvements' (Keetharuth et al., 2018).

Dialog The Dialog Satisfaction Scale gauges 'patient satisfaction' concerning their quality of life and the treatment they receive. This 11-item scale can be analysed item-wise or by calculating a mean score across all items. In this study, an overall mean score will be used, which ranges from 1 to 7. Scores above 5 suggest high satisfaction, potentially indicating that secondary mental health care might no longer be necessary. Conversely, scores below 4 highlight explicit dissatisfaction, warranting "particular attention" (Mosler et al., 2020).

Columbia Scale: The Columbia Suicidality Response Severity Scale (CSRSS) offers a preliminary indication of an individual's suicide risk. It contains 6 items and total or mean scores range from 0 to 1. While it should be used alongside other risk assessment tools, it serves as an initial screening tool for potential suicide risk in adults. The scale has shown sensitivity to changes in suicidality over time (Posner et al., 2011).

3.3 Outcome measures/endpoints

The endpoint for the study's outcome will be at 24 months. This will include 18 months of treatment, and 6 months of follow up.

3.4 Primary endpoint/outcome

Reductions in the LPFS 2.0 and Social Isolation short form 4.0 constitute a potential benefit. We have chosen these outcome measurements as they are used internationally, recommended by ICHOM, and have been validated for use in older adults. We are measuring personality functioning and social isolation as our primary measures. We are making comparisons between baseline functioning, and across participants to power the study. Measurements are taken weekly from start of the waiting period, for the duration of the treatment phase, and at follow up.

The primary endpoint will be whether personality function (as measured by the LPFS 2.0) and social isolation (as measured by the social isolation short form 4.0) have changed during 24 months. Significant decreases in both measures will indicate that MBT is effective at improving personality functioning and decreasing social isolation.

Additionally, if participants had any incidents of suicidal behaviour or self-harm, then a reduction in frequency of these events will constitute a potential benefit. As older people may keep suicidal behaviour and self-harm hidden, there is an expectation that participants may not make disclosures around these issues at baseline.

Taking data pertaining to service use may provide a limited indication as to whether any potential cost savings are associated with the intervention. Due to the limited number of participants, there is a recognition that statistical test on these findings may not reach statistical significance.

Any reduction in self-harm, suicidality, or service use may also represent efficacy.

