3.7 Table of endpoints/outcomes

Objectives	Outcome Measures	Timepoint(s) of evaluation of this outcome measure (if applicable)
Primary Objective Personality Functioning Social isolation	LPFS 2.0. Social Isolation Short Form 4.0	Both questionnaires are given from day 0 till the end of data collection period at 24 months. Patients are requested to fill out these two questionnaires on a weekly basis during waiting period, treatment and follow up.
Service use Self injury and suicidal behaviour	Service use Suicidal behaviour	Data to be taken from clinical records at 0,6,12,18, and 24 months
Feasibility	Comparison of recruitment rate, drop out, and completion	Data to be taken at 0, 6, 12, 18, 24 months
Acceptability	Thematic analysis of qualitative interview	Analysis of data at 24 months
Secondary Objectives		
To evaluate	ReQoL 10	Measures provided at 6 month
quality of life (ReQol),		intervals, at 0,6,12,18, and 24 months.
patient satisfaction (Dialogue),	Dialogue	months.
and suicidality (Columbia Scale).	CSRSS (Columbia Scale)	

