4 TRIAL DESIGN

Design:

This study uses a multiple single case series design, a form of Single Case Design (SCD). It will employ quantitative methods to track changes in personality functioning over time using the LPFS 2.0 scale and changes in loneliness using the Social Isolation Short Form 4a. Data from a participant will be compared within the participant between treatment phases (baseline, treatment and follow up), so participants serve as their own controls. Initial data collection will take place at an outpatient clinic in Manchester, United Kingdom. Data will be gathered weekly away from the MBT clinic. The research team, primarily involved in clinical practice, will utilize an established older adult MBT service in Manchester for the sample. This approach mitigates some challenges of assessing multi-modal

psychological treatments, as there's no need for the research team to establish a new therapy program.

A multiple single case series design will enhance experimental control since participants serve as their own control. In order to get a stable and representative estimate of the baseline state all participants will have a waiting period of 8 weeks before starting treatment. Participants who drop out of the research completely during this phase won't have any further data collected We will ask anyone who drops out of the therapy to consent to providing data relating to their reason for drop out.

The strength of a SCD study is that it produces statistical power by taking a large number of data points with a small number of participants. Due to the high number of data points per participant, change to outcome measurements can accurately be described. Additionally, due to the low number of participants, there is a lower cost to the intervention, which means that it is more feasible to carry out long term studies of psychological treatments for personality disorder, which often span multiple years.

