7.1.1 Participant identification

To guarantee confidentiality, participants will receive both written and verbal information detailing the scope and limitations of confidentiality within the study. Information shared by participants will remain confidential and will not be disclosed to anyone outside the clinical or research team, barring urgent, life-saving circumstances. Outcome measure data will be securely stored, and participants will be allocated a unique identification number to safeguard their identities.

Identification of potential participants will be completed by members of the participants usual clinical team. No further recruitment will take place outside of later life community mental health teams.

Members of the research team will not have prior access to potential participants, who will be referred to the study by the community mental health teams. During the study, the therapists delivering the study intervention will record clinical information on the participants PARIS record, which is the local recording system used by the NHS trust. Outcome measurement data will be pseudonymized and will not be identifiable to members of the clinical team.

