11.2 Data handling and record keeping

Four systems will be used to manage data. The PARIS system for clinical data, a secure database for outcome measures, SPSS software to manage statistics, and the Single Case Designs app to managed data relating to SCD portion of the study.

For clinical data, including records of appointments, and clinical communication, this will be recorded on PARIS, which is the local NHS trust's recording software. Standard local processes will be followed, and adhered to.

Outcome data will be securely stored on a database, validated by the research and development team. The SOPs for the use of the system will be followed, and an audit trail of data changes will be maintained to ensure that there is no deletion of entered data. The system will be secure to protect against unauthorized access. Upon the commencement of the trial, a list of the individuals authorized to make data changes will be compiled. They will be responsible for data entry, maintain adequate backups of the data, and safeguarding the blinding of the trial to the clinical team. Source data will be archived. If data are transformed during processing, it should always be possible to compare the original data and observations with the processed data. Participant identification codes will be used to ensure identification of all the data reported for each participant.

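### Change in recorded self-harm cannot be read as efficacy in either direction: section 3.4 credits reductions only, recording is likely to differ by phase, and there is no control

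*Protocol*

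**What the plan says.** Section 3.1 of the Protocol places self-harm and suicidal behaviour under the primary outcomes, and the table in 3.7 has them in the primary block. The measure is "Incidents of self-harm recorded in the clinical record", together with incidents of self-injury or self-neglect with life-threatening intent. Section 3.7 sets the timing: "Data to be taken from clinical records at 0,6,12,18, and 24 months".

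Section 3.4 gives the reading of the result: "if participants had any incidents of suicidal behaviour or self-harm, then a reduction in frequency of these events will constitute a potential benefit". It then warns that "there is an expectation that participants may not make disclosures around these issues at baseline", and closes with a broader sentence: "Any reduction in self-harm, suicidality, or service use may also represent efficacy". It does not say how an increase, or a first incident after treatment starts, is to be read.

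On the source, section 7.1.1 says that "the therapists delivering the study intervention will record clinical information on the participants PARIS record". Section 11.2 describes the system as "PARIS, which is the local NHS trust's recording software".

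On contact, section 8.1 gives one individual and one group session a week for 18 months, and Appendix 1 lists MBT as twice weekly and CMHT care as monthly at least. Section 4 says that "all participants will have a waiting period of 8 weeks before starting treatment". Section 10.3.1 states that there is no between-group comparison, and section 10.3.2 plans a Friedman test of self-harm across phases.

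**The concern.** With no control group, the claim rests entirely on how a fall or a rise within participants is interpreted. Three influences other than behaviour can move the recorded count.

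- **Baseline.** If incidents are under-disclosed at baseline, as the protocol expects, and disclosure improves in therapy, the recorded count rises with behaviour unchanged. A real reduction can be hidden.
- **Follow-up.** Two sessions a week give many occasions for an incident to be disclosed and written down. When MBT ends, the stated minimum is monthly CMHT contact. A recorded fall in follow-up may reflect fewer such occasions.
- **Selection.** If benefit is judged in those who had a baseline incident, their next count is expected to be lower by chance.

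The rule in 3.4 credits falls and is silent on rises. An ineffective treatment could therefore be reported as promising, and an effective one could look harmful during therapy. Section 2 says the study is to inform a future RCT, so the reading would carry forward.

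**Working it through.** **Inputs.** The protocol gives no self-harm rate, disclosure rate, effect size or power for self-harm, so it has no figure to reproduce. It does not state the look-back period at month 0 either. Assumed throughout:

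- equal windows and no true change in behaviour;
- mean *m* = 0.5, 1 or 2 incidents per person per 6-month window;
- rates that vary between people as a gamma distribution with shape *k* = 0.5 or 1;
- recorded fractions *d*1 in the first window and *d*2 in the second.

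**Step 1: all participants, baseline to treatment.** The ratio of recorded counts is *d*2/*d*1.
- 50% then 80%: 0.8/0.5 = 1.6, a 60% rise.
- 30% then 90%: 0.9/0.3 = 3.0, a 200% rise.
- Equal recording: ratio 1, no change.

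**Step 2: all participants, treatment to follow-up.**
- 80% then 50%: 1 − 0.5/0.8 = 0.375, a 38% fall.
- 80% then 30%: 1 − 0.3/0.8 = 0.625, a 63% fall.

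**Step 3: only participants with a baseline incident, full recording.** For gamma-Poisson counts, the baseline total among the selected has expectation *m* per person enrolled. The later total among the same people has expectation *m*[1 − (1 + *m*/*k*)^−(*k*+1)]. The spurious fall is therefore (1 + *m*/*k*)^−(*k*+1).

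| *m* | *k* = 0.5 | *k* = 1 |
|---|---|---|
| 0.5 | 2^−1.5 = 35% | 1.5^−2 = 44% |
| 1 | 3^−1.5 = 19% | 2^−2 = 25% |
| 2 | 5^−1.5 = 9% | 3^−2 = 11% |

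Simulation with 10 participants agrees to within 1 percentage point. At *m* = 1 the selected group's total fell in 66% to 71% of simulated studies and rose in 20% to 25%. With 50% recording in both windows, replace *m* by 0.5*m*: the range becomes 19% (3^−1.5) to 64% (1.25^−2).

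The result depends on selecting on the baseline window. If the condition is an incident in either of two equal windows with equal recording, the windows are exchangeable and the expected change is zero.

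**Step 4: baseline selection and under-disclosure together.** The ratio is (*d*2/*d*1) × [1 − (1 + *d*1*m*/*k*)^−(*k*+1)]. For 50% then 80%:

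| *m* | *k* = 0.5 | *k* = 1 |
|---|---|---|
| 0.5 | 1.6 × (1 − 0.544) = 0.73, 27% fall | 1.6 × (1 − 0.640) = 0.58, 42% fall |
| 1 | 1.6 × (1 − 0.354) = 1.03, 3% rise | 1.6 × (1 − 0.444) = 0.89, 11% fall |
| 2 | 1.6 × (1 − 0.192) = 1.29, 29% rise | 1.6 × (1 − 0.250) = 1.20, 20% rise |

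The sign of the net bias changes with event and disclosure rates that the study will not know.

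**The case against.** The strongest reply is that the planned analysis is already two-sided. The Friedman test in 10.3.2 has no restriction to participants with incidents and responds to rises as well as falls. The condition in 3.4 may simply recognise that a frequency cannot fall from zero, and it names no period. Worsening is seen elsewhere: life-threatening suicidal behaviour is recorded throughout (9.2), SAEs are reported until 6 months after treatment (9.5), and the Columbia scale, collected by the research assistant (10.8), is judged individually with a Reliable Change Index (10.3.3). MBT staff also meet participants before treatment, in the 12-week introductory group and in the passport and assessment work during baseline. CMHT care continues afterwards, and monthly is only its minimum. The recorded fractions used above are assumptions.

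Much of this stands, and it rules out several stronger readings that a reader might infer.

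- *That the under-disclosed baseline makes reductions appear.* It works the other way, as step 1 shows.
- *That benefit is read only in those with incidents.* The last sentence of 3.4 and the test in 10.3.2 carry no such condition.
- *That the outcome record is the MBT therapists' own.* They are named as contributors to a trust-wide system, not as its sole authors.
- *That selection alone gives falls of 61%, 37% and 14% at 0.5, 1 and 2 incidents.* Those are exp(−*m*), which needs selection on a baseline incident and one rate shared by everyone.

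The reply leaves two gaps. The test does not govern interpretation; 3.4 does, and it credits reductions without saying what an increase means. Nor can a test across phases separate behaviour from recording when both may change with phase.

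**Conclusion.** The point holds as one about interpretability. Recorded self-harm can rise or fall between phases with no change in behaviour, and the design has nothing to separate the causes. The pull is towards a rise from baseline to treatment (60% to 200% under the assumed fractions) and towards a fall in follow-up (38% to 63%). Selection on a baseline incident, if the rule is applied that way, adds a fall of about 9% to 44% at full recording. These sizes are illustrative, because every rate is assumed. The directions need less: that disclosure improves after a baseline the protocol itself expects to be under-disclosed, and that recording opportunity drops when twice-weekly sessions end.

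This should be corrected but does not undermine the study. Section 3.4 defines the primary endpoint by the LPFS and social isolation scores, and its self-harm wording is hedged. The documents do not support a claim that the plan is biased towards showing benefit overall.

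**What to change.** In section 3.4:

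1. State that change in self-harm and suicidal behaviour is judged over all participants, in line with the test in 10.3.2, with increases and first incidents reported alongside decreases.
2. Take self-harm out of the closing sentence on efficacy, and call the comparison descriptive because ascertainment differs by phase.

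In the planned record review, add one field for who first detected each incident (MBT team, CMHT, A&E, crisis line, inpatient or other). Show the phase comparison with and without MBT-detected incidents as a sensitivity analysis.

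Simply excluding MBT therapists' entries would be worse. Section 2.1 has the care coordinator contacted after a risk event, with consent, so an incident first disclosed in therapy can also appear in CMHT entries. Exclusion would not give a constant source, and it would discard events from an outcome likely to be sparse with 10 to 14 participants. That is why the field should capture first detection, not authorship of the entry.

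The cost is a short protocol amendment, one extra extraction field and a less favourable claim about self-harm. No clinical procedure changes.
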